11. STUDY ASSESSMENTS AND PROCEDURES

11.1. Informed Consent Form

Each participant must sign and date a study-specific ICF before any study-specific procedures are performed. The ICF will comply with all applicable regulations governing the protection of participants. An ICF, approved by the Sponsor and the site's Institutional Review Board (IRB), must be used. The Investigator or designee must document the consenting process, including the date when the ICF was signed in the participant's source documents.

Additional information for written consent is provided in Section 13.3.2.

11.2. Randomization/Assigning Participant Number

A unique participant identification number (participant number) will be assigned to each participant once informed consent is obtained. Detailed instructions on assigning participant numbers will be provided in the IRT Manual. If a participant is rescreened, the participant retains the original participant number (see Section 8.6).

11.3. Pre-screening, As Applicable

Participants who require a biopsy to confirm TGCT diagnosis should sign a pre-screen consent form before the biopsy (refer to Section 11.9.2).

11.4. Screening

Screening must occur within 42 days prior to the first dose of study drug to confirm that participants meet the selection criteria for the study. The assessments to be conducted at screening are provided in Table 1. Participants will be enrolled in the study after confirmation of all eligibility criteria and will be randomized to a treatment arm.

11.5. Treatment Period

Duration of treatment is defined in Section 7.4. Treatment period begins when the first dose of study drug is administered in the clinic on Cycle 1 Day 1 in Part 1. Study visits during the treatment period will occur as shown in Table 1, Table 2, and Table 3. All visits must occur within the windows specified.

11.5.1. End of Part 1 Visit

The End of Part 1 visit and the first Part 2 visit both occur at Week 25. The End of Part 1 visit serves as both the last visit of Part 1 and entry into Part 2. The following assessments for the End of Part 1 visit must be performed before unblinding: MRI, ROM, AE Review, Investigator questionnaires, and PRO questionnaires as noted below in Table 12. All End of Part 1 assessments must be completed before dosing in Part 2. After unblinding, the assessments to be completed at the first Part 2 visit are shown in Table 13.

Participants who are unblinded in Part 1 due to confirmed disease progression by IRR and were on placebo will cross over to Part 2, and will need to complete End of Part 1 Assessments per

Table 1. The MRI, ROM assessment, and PRO questionnaires will not need to be repeated if completed within 30 days of End of Part 1 Visit.

Table 12:End of	of Part 1	Visit
-----------------	-----------	-------

End of Part 1 / Week 25		
Assessments	Timing	
 MRI of affected joint^a ROM assessment^b 	 May utilize -7d window and must perform while blinded 	
 AE review Completion of Investigator questionnaires (CGIC/CGIS) PRO questionnaires 	• At End of Part 1 visit and must perform while blinded	
 Review concomitant medications/procedures Full physical exam Vital signs and weight Pregnancy test^c Collection of central safety labs^d Urinalysis 12-lead ECG 	• Must be completed before dosing in Part 2, may be performed while blinded or after unblinding	

Abbreviations: AE=adverse event; CGIC=clinician global impression of change; CGIS=clinician global impression of severity; d=day; ECG=electrocardiogram; MRI=magnetic resonance imaging; PRO=patient-reported outcome; ROM=range of motion.

^a Confirmation that MRI has been performed satisfies unblinding criteria.

^b ROM assessment (active and passive) of both the affected joint and non-affected joint will be performed at the End of Part 1 visit.

^c Pregnancy testing must be done within 3 days of dosing in Part 2.

^d Safety labs to be completed within 3 days of dosing in Part 2

Note: All of the above procedures must be completed as outlined above before dosing in Part 2.

Table 13:First Part 2 Visit

Week 25 Cycle 1 Day 1 Crossover For participants crossing over from placebo		Week 25 Cycle 7 Day 1 For participants who were assigned vimselting in Part 1	
 Predose PK and pharmacodynamic sampling Participant dosing diary instruction/review Narcotics analgesic diary instruction/review Vimseltinib dosing 2 hour postdose PK 	OR	 Predose PK and pharmacodynamic sampling Participant dosing diary instruction/review Narcotics analgesic diary instruction/review Vimseltinib dosing 	

Abbreviation: PK=pharmacokinetics

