9.4.1. Blinding

In Part 1 of the study, the participants and all site personnel, including the Investigator, the site monitor, and the study team must be blinded to study drug treatment, with the exception of the following:

- Any site personnel for whom this information is important to ensure the safety of the participant in the event of a life-threatening medical emergency
- Any site personnel for whom this information is important to ensure the safety of the participant and their fetus in the event of a pregnancy
- Vendors responsible for pharmacovigilance and regulatory personnel at the Sponsor to satisfy serious adverse event (SAE) processing and reporting regulations
- Clinical supply chain personnel at the Sponsor and the vendor
- Unblinded statistician and programmer preparing the final (production) randomization list and unblinded analyses for the data monitoring committee (DMC)
- DMC
- Vendors analyzing PK and biomarker samples
- Vendor conducting the population PK analysis
- IRT vendor
- The Investigator, participant, site personnel, site monitor and study team will become unblinded to a specific participant's treatment assignment, if the participant has disease progression based on IRR or have reached Week 25 and completed End of Part 1 assessments.

9.4.2. Unblinding During Part 1

In exceptional circumstances, emergency unblinding is possible during Part 1 if, in the Investigator's opinion, immediate unblinding of the treatment is necessary for further management of the participant. Participants who are unblinded for emergency will be permanently discontinued from the study.

The Investigator is encouraged to contact the Sponsor or designee and discuss the participant's situation before making the decision to unblind.

Additionally, participants with disease progression confirmed by IRR before completion of Part 1 (ie, Week 25) will be unblinded. Additional information is provided in Section 10.5.

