11.9.14.3.3. Relationship to Study Drug

The assessment of the study drug relationship to each AE will be documented based on the temporal relationship and the best clinical judgment of the Investigator. Causality will be determined using the 2 categories below. All study drugs are considered when defining causality.

• **Related:** The AE is known to occur with the study drug or there is a reasonable possibility that the study drug caused the AE, and there is a temporal relationship

between the study drug and event that supports relatedness. Reasonable possibility means that there is evidence to suggest a causal relationship between the study drug and the AE.

• Not Related: There is no reasonable possibility that the treatment with study drug caused the event, the temporal relationship between the study drug and event onset does not support relatedness, or an alternate etiology has been established.

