11.9.14.3.8. Additional Points to Consider for Adverse Event

11.9.14.3.8.1. Clinically Significant Assessments

Study assessments including laboratory tests, ECGs, physical examinations, and vital signs must be assessed and those deemed as clinically significant must be documented as an AE. When possible, a clinical diagnosis for the study assessment must be provided rather than the abnormal test result alone (eg, urinary tract infection, anemia). In the absence of a diagnosis, the abnormal study assessment itself may be listed as the AE (eg, bacteria in urine or decreased hemoglobin). An abnormal study assessment is considered clinically significant if the patient has 1 or more of the following:

- Worsening, from baseline, concomitant signs or symptoms related to the abnormal study assessment
- Further diagnostic testing or medical/surgical intervention is required
- A change in the dose of study drug, if study drug is withheld, or discontinuation from study drug occurs

Repeat testing to determine whether the result is abnormal, in the absence of any of the above criteria, does not necessarily meet clinically significant criteria. The determination of whether the study assessment results are clinically significant must be made by the Investigator.

A laboratory abnormality judged to be Grade 4, in itself, may not constitute an SAE unless the clinical status of the patient indicates a life-threatening AE.

Symptoms of the disease under study must not be recorded as AEs as long as they are within the normal day-to-day fluctuation or expected progression of the disease, including significant worsening unless the deterioration was unexpected, and are part of the efficacy data to be collected in the study.

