9.11. Safety Analysis

All safety analyses will be conducted on the SAF. If there are both local and central assessments in the same nominal visit, then the central assessment will be used for analyses. The safety data will be summarized following two different approaches. The first approach will be limited to data from Part 1 and will focus on comparisons between participants who received vimseltinib versus participants who received placebo during this period. The second approach will combine data from both Part 1 and Part 2 (including extension period) and will focus on the observations and assessments while participants are receiving vimseltinib. Therefore, in this second approach, participants randomized to Placebo in Part 1 who crossed over to vimseltinib in Part 2, will have as their reference day the first dose date of vimseltinib in Part 2, and their data from Part 1 while receiving placebo will be excluded.

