9.11.4. Electrocardiogram (ECG)

The following ECG measurements will be summarized:

- Heart rate
- RR interval (msec)
- QRS interval (msec)
- QT interval (msec)
- Fridericia corrected QT (QTcF) interval [$QTcF = QT/\sqrt[3]{RR/1000}$]

An overall investigator assessment of ECG will be provided (categories "normal", "abnormal, not clinically significant" and "abnormal, clinically significant"). The following categories will also be reported for QTcF:

- QTcF > 450 msec
- QTcF > 480 msec
- QTcF > 500 msec
- Change from baseline in QTcF > 30 msec
- Change from baseline in QTcF > 60 msec

The ECG measurements and changes from baseline in ECG will be summarized by treatment, visit with descriptive statistics for the SAF.

All ECG data will also be presented in listings.

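### Table 12 allows several Week 25 safety assessments after unblinding, so adverse events first found through them may be judged with the treatment arm known

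*Protocol*

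**What the plan says.** Protocol Section 11.5.1 divides the Week 25 visit by blinding status. Its text states: "The following assessments for the End of Part 1 visit must be performed before unblinding: MRI, ROM, AE Review, Investigator questionnaires, and PRO questionnaires". Table 12 repeats this for the AE review, whose timing is "At End of Part 1 visit and must perform while blinded". A further row of Table 12 covers the concomitant-medication review, full physical exam, vital signs and weight, pregnancy test, central safety labs, urinalysis and ECG. The timing for that row is "Must be completed before dosing in Part 2, may be performed while blinded or after unblinding".

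Other sections read differently. Apart from progression by independent radiological review (IRR), Section 9.4.1 lets the Investigator, participant, site staff, monitor and study team learn an assignment when participants "have reached Week 25 and completed End of Part 1 assessments". Section 9.4.3 uses the same trigger. Neither limits it to a subset of the assessments. Table 1 heads the whole visit column as blinded.

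On who judges findings, Section 11.9.14.3.8.1 makes clinically significant results on labs, ECG, exam or vital signs AEs, and adds: "The determination of whether the study assessment results are clinically significant must be made by the Investigator". Under Section 11.9.14.3.3, relatedness is decided "based on the temporal relationship and the best clinical judgment of the Investigator". SAP Section 9.11 says the Part 1 safety summary "will focus on comparisons between participants who received vimseltinib versus participants who received placebo during this period". SAP Section 9.11.4 adds: "An overall investigator assessment of ECG will be provided", in three categories from normal to abnormal and clinically significant.

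**The concern.** A blinded AE review can cover only what is known when it takes place. If the exam, vital signs, ECG or urinalysis follows unblinding, a finding first made there did not exist at the review. The Investigator then decides whether it is clinically significant, and so an AE, and whether it is related, with the arm known. The Week 25 ECG category can be assigned in the same state.

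Part 1 is the trial's only randomized, placebo-controlled comparison of harms. Knowledge of the arm could plausibly lead to more findings being recorded and attributed on vimseltinib and fewer on placebo. The procedures in question are also where known signals appear. Of the Grade 3 or higher events listed in Protocol Section 5.2 for more than one TGCT patient, raised CPK (33.3%) and raised AST (4.6%) are found by labs in Table 14, and hypertension (4.6%) by vital signs. Under Section 11.9.14.3.3, whether an event is already known to occur with the drug is one ground for calling it related, so knowing the arm bears directly on that call.

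**Working it through.** The plan states no figure on this point, so the check sets passages side by side and counts visits.

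**1. Does the protocol agree with itself?** Sections 9.4.1 and 9.4.3 put completion of the End of Part 1 assessments before unblinding, and the Table 1 header agrees. Table 12 lets some of those assessments follow unblinding. Two footnotes support Table 12: its footnote a treats confirmation that the MRI was done as meeting the unblinding criteria, and Table 1 footnote d refers only to the assessments required to be blinded. Sites following Section 9.4 and sites following Table 12 could therefore act differently.

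**2. Would the resulting AEs count in Part 1?**
- For Part 1: Section 11.5.1 calls the visit the last of Part 1 (and also the entry to Part 2). The procedures must precede Part 2 dosing. Table 13 does not list them for the first Part 2 visit. SAP Section 9.2 defines entering Part 2 by receipt of at least one Part 2 dose.
- Against: Protocol Section 12.4.1 and SAP Section 9.1 describe the open-label portion as what occurs after unblinding at Week 25.

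Part 1 is the likelier reading, but no sentence assigns a finding made after unblinding and before the first Part 2 dose. If such findings were kept out of Part 1, those in placebo participants would also fall outside the SAP's second safety presentation, which covers only time on vimseltinib.

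**3. How many scheduled checks could be affected?** These are Table 1 counts for a participant who completes Part 1:
- Vital signs, ECG, hematology, chemistry: C1D15, C2D1 to C6D1 and Week 25, so 1 + 5 + 1 = 7 post-baseline checks. Week 25 is 1/7 = 14.3%.
- Coagulation, urinalysis: C2D1 to C6D1 and Week 25, so 5 + 1 = 6. Week 25 is 1/6 = 16.7%.
- Full physical exam: Week 25 is the only scheduled post-baseline one in Part 1; other visits have symptom-directed exams.

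Let u be the share of participants whose Week 25 check is done after unblinding. The documents do not give u, so a range is shown. The exposed share of checks is u/7 or u/6:

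| u (assumed) | u/7 | u/6 |
|---|---|---|
| 0 | 0% | 0% |
| 0.5 | 7.1% | 8.3% |
| 1 | 14.3% | 16.7% |

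These are shares of scheduled checks, not of AEs. Turning them into AEs would need finding rates by visit and the effect of unblinding on judgement, and the documents give neither.

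**4. Which tables could move?** SAP Section 9.11.2 counts a participant once per preferred term, so a repeat of a term recorded earlier adds nothing to incidence. The relationship analysis takes the occurrence with the strongest relationship to study drug, and Protocol Section 11.9.14.3.4 has a change in severity reported as a new AE. One related call at Week 25 can therefore override earlier blinded unrelated calls for that term. The drug-related tables are the more sensitive ones.

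**5. Is Week 25 the only unblinded point in Part 1?** No. Sections 9.4.2 and 10.5 unblind participants with IRR-confirmed progression before Week 25. Placebo participants in that position complete the End of Part 1 assessments afterwards, so even their AE review can be unblinded.

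**The case against.** The strongest reply is that Table 12 protects what matters. The MRI, range-of-motion and patient-reported assessments must precede unblinding, so the primary and key secondary endpoints are safe from this row. AEs already known at the blinded review are protected too. Clinical significance is tied to listed criteria in Section 11.9.14.3.8.1. Laboratory summaries, CTCAE shift tables and QTcF categories rest on measured values. Safety is descriptive and lies outside the testing hierarchy. All of this stands and limits the point to a modest one. It does not close the gap: the listed criteria are still applied by the Investigator, and no rule covers a finding first made after the blinded review.

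It is also fair that moving the lab draw does not by itself secure blinded judgement, because central results may return after unblinding whenever the blood was taken. That is why a flag is needed as well.

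Three stronger readings are tempting, and the documents do not support them:
- That Week 25 AEs are in fact judged unblinded. Table 12 allows either order, and nothing says how often sites use the later one.
- That 14 to 17% of AEs are compromised, or that a between-arm bias can be stated in percentage points. The fractions are ceilings on scheduled checks, and the inputs for any bias figure are absent.
- That every judgement before Week 25 is blind. Early unblinding for IRR-confirmed progression contradicts this.

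**Conclusion.** The concern holds in limited form. Table 12 permits the Week 25 exam, vital signs, ECG, urinalysis and safety-lab draw after unblinding, in conflict with Sections 9.4.1 and 9.4.3 and the Table 1 header. AE status and relatedness for findings first made then, and the Investigator's ECG category, may be judged with the arm known. That these AEs enter the placebo-controlled comparison is probable and rests on reading the visit as part of Part 1.

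The exposure is one visit: at most 1 of 7 or 1 of 6 scheduled checks, and less if sites work blinded. The direction suggested above is a judgement, and the size of any effect cannot be derived from the documents. Measured values and efficacy endpoints are untouched. The change is worth making because it is cheap, removes a possible bias from the only controlled safety comparison and resolves an internal conflict.

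**What to change.** **Protocol.** In Table 12, move the full physical exam, vital signs, ECG and urinalysis to the group that must be done blinded, ahead of the AE review. Move the lab draw too where the existing 3-day window allows. Require clinical significance, AE status and relatedness for their findings to be recorded before unblinding. This reconciles Table 12 with Sections 9.4.1 and 9.4.3 and Table 1.

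**SAP.** State that AEs first identified after unblinding but before the first Part 2 dose belong to Part 1. Flag them, including those from late central lab results and those in participants unblinded early for IRR-confirmed progression. Show the Part 1 drug-related treatment-emergent AE table with and without the flagged events.

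**Cost.** Slightly less flexibility on the visit day, one eCRF flag and one extra table. No procedure or participant is added; the work already done at this visit is reordered.

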11.6. End-of-Treatment Visit

Part 1 Double-blind

Participants who discontinue study drug in Part 1 should return for an EOT visit within 7 days of the decision to stop study drug and should complete EOT assessments **as outlined in Table 1**. The MRI and ROM assessments will not need to be completed if performed within the previous 30 days.

Part 2 Open Label

Participants who discontinue study drug should return for an EOT visit within 7 days of the decision to stop study drug. At a scheduled clinic visit, if treatment is not given and it becomes evident that open-label study drug will be discontinued, this visit may become the EOT visit.

11.7. Safety Follow-up Visit

Participants will be required to attend a clinic visit 30 days (± 5 days) after receiving their last dose of study drug or before the start of new TGCT therapy (including radiation or surgery), whichever occurs first. If a participant has been off study drug for more than 30 days at the time of decision to stop treatment, then the Safety Follow-up Visit will be conducted at the EOT visit. The assessments to be conducted at these visits are provided in the relevant schedule of assessments.

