11.9.14.3.9. Monitoring and Recording Adverse Events

The AE (including SAEs) reporting period will begin after a participant signs the main ICF and will continue until completion of the Safety Follow-up Visit or 30 days after the final dose of study drug. Any SAE having an onset after the Safety Follow-up Visit will not be collected or reported unless the Investigator feels that the event may be related to the study drug. Only SAEs that are assessed by the Investigator as related to the biopsy will be collected after a participant signs the pre-screening consent and until the participant has signed the main ICF.

Participants will be instructed by the Investigator or designee to report the occurrence of any AE. All volunteered, elicited, and observed AEs are to be recorded.

If a participant begins a new TGCT therapy, the safety reporting period ends at the time the new treatment is started; however, death must always be reported when it occurs during the safety reporting period irrespective of intervening treatment.

The Investigator will assess all AEs regarding any causal relationship to the study drug, the intensity (severity) of the event, action taken, and participant outcome (see Section 11.9.14.3).

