12.4.6. Safety Analyses

Participants from the Safety Set will be included in safety analyses.

AEs will be coded using the MedDRA for purposes of summarization. All AEs occurring on study will be listed in by participant data listings. Treatment-emergent AEs will be tabulated, where treatment emergent is defined as any AE that occurs after administration of the first dose of study drug and through 30 days after the last dose of study drug. Tabulations for all TEAEs, treatment-emergent SAEs, related TEAEs, dose reduction, dose interruptions, and discontinuation of study drug due to AE will be produced. By participant listings will be provided for deaths, SAEs, and AEs leading to discontinuation of study drug.

Change from baseline in clinical laboratory parameters will be summarized across time on study, and the frequency of clinically significant abnormal laboratory values will be tabulated.

Changes in ECG intervals (QT, RR, QTcF, HR, QRS) and vital sign parameters (including systolic and diastolic blood pressure, heart rate, respiration rate, and temperature) will be summarized over time in a similar fashion to laboratory parameters, and any abnormal values will be tabulated. Changes in ECG findings will be presented in data listing format.

Additional safety assessments such as ECGs will be listed by participant.

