9.11.2. Adverse Event

Adverse events (AEs) will be coded using MedDRA version 26.0 (or higher). The intensity of AE will be documented using the National Cancer Institute (NCI) Common Terminology Criteria for Adverse Event (CTCAE) version 5.0.

A treatment-emergent AE (TEAE) is defined as any AE that occurs or worsens after administration of the first dose of study drug and through 30 days after the last dose of study drug or the day before the start of new antitumor therapy. Drug-related AEs reported after 30 days following the last dose of study drug will also be considered as treatment-emergent.

Drug related AEs include AEs reported as 'POSSIBLY RELATED' and 'RELATED'.

Summary statistics (frequency and percentages of participants) will be presented by SOC and PT by treatment group for following:

- Overall summary of TEAEs
- Any TEAE
- Any nonserious TEAE
- Any Grade 3/4 TEAE
- Any serious TEAE

- Any drug-related TEAE
- Any Grade 3/4 drug-related TEAE
- Any drug-related serious TEAE
- Any TEAE leading to dose modification (including dose reduction and interruption)
- Any drug-related TEAE leading to dose modification (including dose reduction and interruption)
- Any TEAE leading to treatment discontinuation
- Any drug-related TEAEs leading to treatment discontinuation
- Any TEAE leading to death

The following will be tabulated by SOC, PT, and maximum severity grade:

- TEAEs
- Serious TEAEs
- Drug-related TEAEs
- Drug-related serious TEAEs

The following will be presented by PT:

- TEAEs
- TEAEs of Grade 3/4
- Serious TEAEs
- Drug-related TEAEs
- Drug-related TEAEs of Grade 3/4
- Drug-related serious TEAEs

If a SOC or PT was reported more than once for a participant, the participant would only be counted once in the incidence for that SOC or PT. For participants experiencing the same PT at multiple severity levels, the occurrence of the AEs with the maximum severity will be counted in the analysis of incidence by severity. For participants experiencing the same PT at multiple relationship levels, the occurrence of the AEs with the strongest relationship to study drug will be counted in the analysis of incidence by relationship to study drug.

The following listings will be provided for the SAF:

- All AEs (including AEs occurring prior and after the TEAE period)
- Serious Adverse Events
- Death
- AEs leading to study drug discontinuation
- AEs leading to dose modification (reduction or interruption)

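### The end of adverse event collection is defined inconsistently and can fall before the end of the treatment-emergent window

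*Protocol*

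**What the plan says.** **Timing of the visit.** Protocol 11.7: "Participants will be required to attend a clinic visit 30 days (± 5 days) after receiving their last dose of study drug". If a new treatment for TGCT is to begin sooner than that, the visit is brought forward to precede it, and no minimum interval then applies. "If a participant has been off study drug for more than 30 days at the time of decision to stop treatment", the visit is held at the EOT visit instead.

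**Collection.** The AE rows of protocol Tables 1, 2 and 3 run through Safety Follow-up and give no day. Protocol 11.9.14.3.9 makes three statements:
- The reporting period "will continue until completion of the Safety Follow-up Visit or 30 days after the final dose of study drug", with no rule for which of the two applies.
- "Any SAE having an onset after the Safety Follow-up Visit will not be collected or reported unless the Investigator feels" it may be related to study drug.
- "If a participant begins a new TGCT therapy, the safety reporting period ends at the time the new treatment is started"; deaths within the reporting period are reported regardless.

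**Analysis.** Protocol 12.4.6 counts as treatment-emergent any AE from the first dose "through 30 days after the last dose of study drug". SAP 9.11.2 counts any AE "through 30 days after the last dose of study drug or the day before the start of new antitumor therapy", and adds drug-related AEs reported after Day 30. Up to Day 30 neither definition depends on causality or on the visit date. The incidence of TEAEs and of treatment-emergent SAEs is a secondary endpoint (protocol 6.2, SAP 4.3).

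**The concern.** The analysis window is fixed by calendar days from the last dose. The collection window is tied partly to a visit that may come before that day. When it does, part of the window being tabulated may not have been observed, and whether an SAE in that stretch reaches the database turns on the visit date and on the investigator's view of causality. The all-causality TEAE and serious TEAE tables would then be incomplete for some participants who stopped drug, and nothing in the output would show it.

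**Working it through.** The plan states no figure for this point, so there is none to reproduce. The check is day arithmetic and a comparison of the texts.

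**Inputs.** Visit day v: 30 ± 5, so Day 25 to Day 35 (protocol 11.7). End of the treatment-emergent window without new therapy: Day 30 (protocol 12.4.6, SAP 9.11.2). Part 1 treatment: 24 weeks = 168 days (protocol 7.1).

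**Step 1: gap for a visit inside its window, if collection stops at the visit.** Gap(v) = max(0, 30 − v).

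| Visit day | Days not collected | Share of 30 post-dose days |
|---|---|---|
| 25 | 5 (Days 26 to 30) | 16.7% |
| 26 | 4 | 13.3% |
| 27 | 3 | 10.0% |
| 28 | 2 | 6.7% |
| 29 | 1 | 3.3% |
| 30 to 35 | 0 | 0% |

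If visits spread evenly over the 11 days from 25 to 35 (an assumption), the mean gap is (5 + 4 + 3 + 2 + 1)/11 = 15/11 = 1.36 days, or 1.36/30 = 4.5% of the post-dose period, and 5 of 11 visits leave any gap. The worst case of 5 days is 5/(168 + 30) = 2.5% of the whole treatment-emergent window of a participant treated for 168 days. A visit held at EOT after more than 30 days off drug leaves no gap.

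**Step 2: does the alternative Day 30 end-point close the gap?** Suppose the *or* in 11.9.14.3.9 means the later of the two dates. Non-serious AEs up to Day 30 then fall inside the reporting period. The SAE sentence does not move, because it is tied to the visit and not to the end of the period. An unrelated SAE on Day 28 after a Day 25 visit is still excluded by that sentence, yet is a serious TEAE under both analysis definitions.

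**Step 3: would later contacts recover the event?** The next scheduled contact is the first Disease Follow-up Visit, 12 weeks ± 4 weeks after the last dose, so no earlier than (12 − 4) × 7 = Day 56. Only related SAEs are reportable during that follow-up (protocol 11.8), and participants with radiologically confirmed progression do not have it (protocol 10.5 and 11.8). The schedule does not prompt for an unrelated event in the gap.

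**Step 4: new therapy on Day t, with t at or before Day 30.** The SAP window closes on Day t − 1. If the new-therapy sentence governs, collection runs to Day t and the gap against the SAP is 0. If the visit governs, the gap is t − 1 − v days. The protocol 12.4.6 definition has no new-therapy cut-off, so Days t to 30 lie inside its window after the reporting period has ended. The two analysis definitions therefore differ from each other as well as from the collection rules.

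**The case against.** The best reply is that the protocol can be read so that almost nothing is lost. Section 11.9.14.3.9 does offer 30 days after the final dose as an end-point. Section 11.9.9 equates Safety Follow-up with 30 days after the last dose, which would give the AE rows of Tables 1 to 3 the same meaning. Section 11.9.14.4.1 requires every SAE in the reporting period to be reported regardless of causality. This stands to the extent that a reader who infers that all collection plainly stops at the visit goes beyond the text, which is ambiguous for non-serious events. It does not dispose of the SAE sentence (Step 2), and equating the visit with Day 30 does not fit a window of ± 5 days.

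Three other stronger readings are tempting and are not supported:
- **A gap of weeks before new therapy.** With a visit on Day 10 and surgery on Day 28, Days 11 to 27 (17 days) could appear lost. Those dates are hypothetical, and the gap is 0 if the new-therapy sentence governs. The text leaves open which sentence governs, so 17 days cannot be given as the size of the problem.
- **Everyone who stops drug is affected.** Visits on Day 30 or later leave no gap. The 15% dropout in protocol 12.1 is a sample-size assumption, not a rate of stopping drug or of early visits. Even if it were used, 0.15 × 120 = 18 participants × 15/11 days gives about 25 person-days, against 120 × 168 = 20,160 planned treatment days in Part 1.
- **Those who stop are the likeliest to have events.** Nothing in the documents shows this.

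It is also fair to say that a ± 5-day visit window is ordinary. The fault lies in the reporting rules, not in the visit window.

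**Conclusion.** The inconsistency is real and minor. The end of AE collection has several unranked definitions, and one explicit rule excludes events that the analysis counts. What is exposed is unrelated SAEs and, if Tables 1 to 3 are read as ending at the visit, non-serious AEs. Related SAEs are not lost, because they remain reportable after the visit.

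For a visit inside its window the loss is at most 5 of 30 post-dose days. The mean of about 1.4 days rests on an even spread of visits, which the documents neither state nor contradict. It applies only to participants seen before Day 30 with part of the window still to run. SAP 9.11 also pools Part 1 with Part 2 and the extension, so the same gap can recur when participants stop later; the documents give no stopping rate from which to size that. The case for acting is that the contradiction touches a secondary safety endpoint and is cheap to remove, not that it could change the safety conclusions materially.

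**What to change.** 1. In protocol 11.9.14.3.9 and the AE rows of Tables 1 to 3, state that all AEs and SAEs, regardless of causality, are collected through the later of the Safety Follow-up Visit and 30 days after the last dose, or until new TGCT therapy starts if that is earlier. A rule based on the earlier of visit and Day 30 would not serve: it would keep the gap after an early visit and drop events up to a visit on Days 31 to 35.
2. Tie the sentence excluding later unrelated SAEs to the end of that period instead of to the visit. Keep the existing rules on deaths and on related SAEs after the period.
3. Align the TEAE definition in protocol 12.4.6 with SAP 9.11.2, including the new-therapy cut-off and the drug-related events reported after Day 30. Events collected on Days 31 to 35 that are not drug-related would appear in the listing of AEs outside the TEAE period that SAP 9.11.2 already plans.
4. For visits already held, report how many fell before Day 30 with window remaining, so that the size of any loss is visible.

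The cost is protocol wording and a brief telephone check at the end of the window for participants whose visit came earlier. No efficacy analysis or treatment rule changes.
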